8.7. Genetics

A whole blood sample will be collected for pharmacogenetic analysis as specified in the Schedule of Activities (Section 1.3) where local regulations allow.

Samples will not be used to conduct unspecified disease or population genetic research either now or in the future. Samples will be used to investigate variable response to tirzepatide and to investigate genetic variants thought to play a role in obesity. Assessment of variable response may include evaluation of AEs or differences in efficacy.

All samples will be coded with the participant number. These samples and any data generated can be linked back to the participant only by the investigator site personnel.

Samples will be retained at a facility selected by Lilly or its designee for a maximum of 15 years after the last participant visit for the study, or for a shorter period if local regulations and/or ethical review boards (ERBs)/IRBs impose shorter time limits. This retention period enables use of new technologies, response to regulatory questions, and investigation of variable response that may not be observed until later in the development of tirzepatide or after tirzepatide becomes commercially available.

Molecular technologies are expected to improve during the 15-year storage period and therefore cannot be specifically named. However, existing approaches include whole genome or exome sequencing, genome wide association studies, and candidate gene studies. Regardless of technology utilized, genotyping data generated will be used only for the specific research scope described in this section.

8.8. Biomarkers

Biomarker research is performed to address questions of relevance to drug disposition, target engagement, PD, mechanism of action, variability of participant response (including safety), and

clinical outcome. Sample collection is incorporated into clinical studies to enable examination of these questions through measurement of biomolecules including deoxyribonucleic acid (DNA), proteins, lipids, and other cellular elements.

Serum, whole blood, and plasma samples for biomarker research will be collected at the times specified in the Schedule of Activities (Section 1.3) where local regulations allow.

Samples will be used for research on the drug target, disease process, variable response to tirzepatide, pathways associated with obesity, mechanism of action of tirzepatide, and/or research method or in validating diagnostic tools or assay(s) related to obesity.

All samples will be coded with the participant number. These samples and any data generated can be linked back to the participant only by the investigator site personnel.

Samples will be retained at a facility selected by Lilly or its designee for a maximum 15 years after the last participant visit for the study, or for a shorter period if local regulations and ERBs/IRBs impose shorter time limits. This retention period enables use of new technologies, response to regulatory questions, and investigation of variable response that may not be observed until later in the development of tirzepatide or after tirzepatide become(s) commercially available.

8.9. Immunogenicity Assessments

At the visits and times specified in the Schedule of Activities (Section 1.3), venous blood samples will be collected to determine antibody production against tirzepatide.

To interpret immunogenicity results, a venous blood sample will be collected at the same time points to determine the blood concentration of tirzepatide. All samples for immunogenicity should be taken predose when applicable and possible. The actual date and time (24-hour clock time) of each sampling will be recorded. Immunogenicity will be assessed by a validated assay designed to detect ADAs in the presence of tirzepatide at a laboratory approved by the sponsor. Antibodies may be further characterized for cross-reactive binding to endogenous counterparts, and their ability to neutralize the activity of tirzepatide or endogenous counterparts. Sample collected at Visit 801 will assess immunogenicity at washout of tirzepatide (5 half-lives post end of treatment).

Treatment-emergent ADAs are defined in Section 9.4.5.

Long-term sample retention is defined in Section 10.1.11.

8.10. Health Economics and Medical Resource Utilization

Health Economics/Medical Resource Utilization and Health Economics parameters are not evaluated in this study.

9. Statistical Considerations

9.1. Statistical Hypotheses

The alternative hypotheses for the primary objective are the following:

- H_{10} : QW tirzepatide 10 mg is superior to placebo for percent change in body weight from randomization AND percentage of participants who achieve $\geq 5\%$ body weight reduction at 72 weeks.
- H₁₅: QW tirzepatide 15 mg is superior to placebo for percent change in body weight from randomization AND percentage of participants who achieve ≥5% body weight reduction at 72 weeks.

The above 2 hypotheses will be tested in parallel, each at a 2-sided significance level of 0.025.

9.2. Sample Size Determination

Approximately, 348 participants will be screened to achieve 261 randomly assigned to study intervention (approximately 87 participants per intervention group).

The sample size determination assumes that evaluation of superiority of tirzepatide 10 mg and tirzepatide 15 mg to placebo will be conducted in parallel, each at a 2-sided significance level of 0.025 using a 2-sample t-test. Additionally, a difference of at least 11% mean body weight percentage reduction from randomization at 72 weeks for tirzepatide 10 mg and/or tirzepatide 15 mg compared with placebo, a common SD of 10%, and a dropout rate of 25% are assumed for statistical power calculations. Under the assumptions above, randomizing 261 participants in a 1:1:1 ratio to tirzepatide 10 mg, tirzepatide 15 mg, and placebo provides more than 90% power to demonstrate superiority of each tirzepatide dose to placebo.

The chosen sample size and randomization ratio also provides >90% power to establish superiority of tirzepatide 10-mg and/or tirzepatide 15-mg doses to placebo in terms of proportion of participants achieving at least 5% body weight reduction at 72 weeks, conducted in parallel using a Fisher's exact test, each at a 2-sided significance level of 0.025, assuming 25% of placebo-treated participants and 90% of tirzepatide-treated participants achieve the goal and a dropout rate of 25%.

9.3. Populations for Analyses

The following populations are defined:

Population	Description
Entered Participants	all participants who sign the informed consent form (ICF)
Randomized Participants	all participants who are randomly assigned to treatment
Modified Intent-to-Treat (mITT) Set	all randomly assigned participants who are exposed to at least 1 dose of study drug; participants will be included in the treatment group they were randomized to
Efficacy Analysis Set (EAS)	data obtained during treatment period from mITT, excluding data after discontinuation of study drug (last dose date +7 days)
Full Analysis Set (FAS)	data obtained during treatment period from mITT, regardless of adherence to study drug
Safety Analysis Set (SS)	data obtained during the treatment period plus safety follow-up period from mITT, regardless of adherence to study drug

9.4. Statistical Analyses

9.4.1. General Considerations

Statistical analysis of this study will be the responsibility of Lilly or its designee. Any change to the data analysis methods described in the protocol will require an amendment ONLY if it changes a principal feature of the protocol. Any other change to the data analysis methods described in the protocol, and the justification for making the change, will be described in the statistical analysis plan (SAP) or the clinical study report. Additional exploratory data analyses may be conducted as deemed appropriate.

Unless otherwise noted, all tests of treatment effects will be conducted at a 2-sided alpha level of 0.05, and the confidence interval will be calculated at 95%, 2-sided. In statistical summaries and analyses, data will be analyzed as randomized.

Unless specified otherwise, efficacy and safety will be assessed using the modified intent-to-treat (mITT) population. Baseline is defined as the last nonmissing data collected at randomization (prior to first dosing of study drug). Unless specified otherwise, safety assessments will be guided by an estimand comparing safety of tirzepatide doses with placebo irrespective of adherence to study drug. Thus, safety analysis will be conducted using SS.

Summary statistics for continuous measures will include sample size, mean, SD, median, minimum, and maximum. The analysis model to make comparisons among treatment groups relative to continuous measurements assessed over time will be a mixed model for repeated measures (MMRM), with terms of treatment, visit, and treatment-by-visit interaction, stratification factors, and baseline measurement as a covariate.

Kaplan-Meier method will be used for estimation of cumulative event-free survival rates over time, and Cox proportional hazards regression analysis will be used to compare hazard rates among treatments.

Summary statistics for categorical measures (including categorized continuous measures) will include sample size, frequency, and percentages. Logistic regression will be used to examine the treatment difference in binary efficacy outcomes if there is a need to adjust for covariates. Otherwise, Fisher's exact test will be used to examine the treatment difference in categorical outcomes.

Summary statistics for discrete count measures will include sample size, mean, SD, median, minimum, and maximum. The negative binomial regression model will be used for the treatment comparison of discrete count measures.

Other statistical methods may be used, as appropriate, and details will be described in the SAP.

9.4.2. Treatment Group Comparability

9.4.2.1. Participant Disposition

A detailed description of participant disposition will be provided at the end of the study.

Frequency counts and percentages of all participants screened, randomized, and receiving at least 1 dose of study drug will be presented by treatment groups. Of the participants in the mITT set, frequency counts and percentages of participants who completed the study, prematurely discontinued the study (and/or study drug), including reason for premature discontinuation, will be presented by treatment groups.

A Kaplan-Meier analysis of the following time periods by treatment group will be provided

- time from randomization to premature discontinuation from study, and
- time from randomization to premature discontinuation from study treatment.

9.4.2.2. Participant Characteristics

Demographics and other baseline characteristics related to obesity disease including comorbidities of 11 obesity-related health problems defined by JASSO guidelines in Appendix 13 (Section 10.13), socioeconomic status (such as employment status and length of education), and day life environment (such as marital and living status) will be summarized by treatment group for all randomized participants.

9.4.2.3. Concomitant Therapy

Concomitant medications, including previous therapy, will be summarized by treatment arm for SS.

9.4.2.4. Treatment Compliance

Frequency counts and percentages of participants compliant to study drug will be summarized by treatment groups and visits for FAS.

9.4.3. Efficacy Analyses

9.4.3.1. Primary Analyses

The primary efficacy analysis will be guided by the "efficacy" estimand, which represents efficacy prior to discontinuation of study drug under missing at random assumption. The efficacy analyses will be conducted using the EAS. The primary analysis model will be a MMRM for body weight percentage change over time and longitudinal logistic regression for proportion of participants achieving at least 5% body weight reduction over time. The response variable of MMRM will be the percent change in body weight from baseline values obtained at each scheduled postbaseline visit. The response variable of longitudinal logistic regression will be the achievement of at least 5% body weight reduction at each scheduled postbaseline visit. The independent variables of both analysis models are treatment group (tirzepatide 10 mg, tirzepatide 15 mg, and placebo), visit, and treatment by visit interaction, stratification factors: baseline IGT (yes or no); baseline hyperlipidemia (based on TG; yes or no); baseline NAFLD (yes or no) and sex (female, male), and baseline body weight as a covariate. An unstructured covariance structure will model relationship of within-patient errors. The Kenward-Roger approximation will be used to estimate denominator degrees of freedom. Since the mean percent change in body weight and the percentage of participants with $\geq 5\%$ body weight reduction needs to be achieved at the same time, no multiplicity adjustment is planned for these 2 tests.

For the supplemental purpose, sensitivity analysis of the primary efficacy analysis will be performed that will be guided by the "treatment-regimen" estimand and conducted using the FAS, which represents efficacy regardless of adherence to study drug. This assessment will analyze percent change in body weight obtained at the 72-week visit using an analysis of covariance (ANCOVA) and the percentage of participants achieving at least 5% body weight reduction obtained at the 72-week visit using a logistic regression model. Both models will include terms of treatment, stratification factors, and baseline body weight as a covariate. Missing value of change in body weight at the 72-week visit will be imputed based on observed body weight change from baseline values at the visit from participants in the same treatment group who had their efficacy assessed after early discontinuation of study drug. In cases where there are not enough retrieved dropouts to provide a reliable imputation model (for example, the model implemented by the SAS program does not converge), an alternative multiple imputation method with reference to the placebo group (placebo multiple imputation) will be used. Analysis will be conducted with multiple imputations.

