9.4.3.2. Secondary Analyses

Proportion of participants who achieved improvement of obesity-related health problems (IGT, hyperlipidemia, or NAFLD) for each treatment group will be compared based on "efficacy" estimand using EAS. For improvement of each obesity-related health problem, composite endpoints (improvement of >1 obesity-related health problem), logistic regression analysis with treatment and sex as factor will be used. For improvement of hyperlipidemia and other categorical efficacy endpoints, longitudinal logistic regression will be used.

Other continuous efficacy endpoints will be analyzed using a MMRM model.

Additional details will be provided in the SAP.

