#### 2.1. Multiplicity Adjustment

The type 1 error will be controlled in the strong sense at a two-sided significance level of 0.05 because two hypotheses ( $H_{10}$  and  $H_{15}$ ) will be tested in parallel each at a 2-sided significance level of 0.025. Since superiority of each one of two hypotheses will be declared if and only if both statistical tests (regarding percent change in body weight and percentage of participants who achieve  $\geq$ 5% body weight reduction) are significant, no multiplicity adjustment is planned for these 2 tests.

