#### 4.3.2.2. Main Analytical Approach for Categorical Measures

For the percentage of participants achieving at least 5% body weight reduction from randomization over time, a logistic regression model will be used with the response variable of the percentage of participants achieving at least 5% body weight reduction at each scheduled postbaseline visit.

A logistic regression model with terms of treatment group stratification factors: baseline IGT (yes or no); baseline hyperlipidemia (based on TG; yes or no); baseline NAFLD (yes or no) and sex (female, male) as fixed effects, and baseline body weight as a covariate, will be conducted for percentage of participants achieving at least 5% body weight reduction from randomization at the 72 week visit. Missing body weight measurement at 72 week will be imputed by the predicted value from MMRM model aforementioned, then the continuous measurements will be dichotomized into status of achieving at least 5% body weight reduction (Yes or No). A logistic regression will be utilized to analyze proportion of participants with at least 5% body weight reduction at each nominal visit from randomization through 72 weeks.

With the aid of the logistic regression model, 2-sided 95% CI and odds ratio for percentage of participants achieving at least 5% body weight reduction from baseline to the 72-week visit between tirzepatide 10 mg or 15 mg QW and placebo will be derived.

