# 4.9. Changes to Protocol-Planned Analyses

Efficacy analysis set for imaging data has been modified to accommodate the allowance of measurement schedule.

Added following exploratory objectives:

- Improvement of hyperuricemia (defined by uric acid ≤7.0 mg/dL).
- Improvement of hypertension: Diastolic blood pressure <80 mmHg or Systolic blood pressure <130 mmHg.
- Achievement of ALT ≤30 U/L.
- Changes in NAFLD fibrosis score.

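### Protocol and SAP give different models and missing-data rules for the ≥5% responder co-primary, and SAP 4.9 does not record the difference

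*Protocol*

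**What the plan says.** Protocol 9.4.3.1 names the primary responder analysis as "longitudinal logistic regression for proportion of participants achieving at least 5% body weight reduction over time". The response is the yes/no status at each scheduled post-baseline visit. The model has treatment, visit and treatment-by-visit terms, the four stratification factors and baseline weight. The efficacy estimand is analysed under missing at random, and no imputation is described for it.

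SAP 4.3.2.2 begins its model as "A logistic regression model with terms of treatment group stratification factors: baseline IGT (yes or no" and continues with the other three strata and baseline weight, fitted at Week 72. It has no visit or treatment-by-visit term and no within-patient covariance. A missing Week 72 weight is replaced by the value predicted from the MMRM, and the completed weights are then dichotomised. SAP 4.1 confirms that missing Week 72 values are handled by Section 4.3.2. Section 4.3.2.2 also says that a logistic regression will be run at each nominal visit.

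On changes, SAP Section 1 sends the reader to 4.9. That section opens with "Efficacy analysis set for imaging data has been modified to accommodate the allowance of measurement schedule" and then lists four added exploratory objectives. It does not mention the responder model or its imputation. Protocol 9.4.1 says that a method change "will require an amendment ONLY if it changes a principal feature of the protocol"; any other change, with its justification, goes in the SAP or the clinical study report.

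On the decision, Protocol 9.1 states: "The above 2 hypotheses will be tested in parallel, each at a 2-sided significance level of 0.025". SAP 2.1 adds that "superiority of each one of two hypotheses will be declared if and only if both statistical tests" are significant.

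**The concern.** The responder p-value is one of the two that decide each dose. SAP 2.1 makes no adjustment between the two co-primary tests, and that is sound only if each is a prespecified test that holds its 0.025 level. Here the two governing documents describe different tests with different treatment of dropouts, and nothing says that one replaced the other or why. The published odds ratio and confidence interval depend on which is run. The SAP version also treats a single filled-in value as if it had been observed, which understates uncertainty. The SAP does not say whether the prediction is subject-level (using that participant's earlier weights) or arm-level.

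**Working it through.** **1. Is this only loose wording?** No; both documents treat the two models as distinct methods.
- Protocol 9.4.3.1 assigns a Week 72 logistic model to the supplementary treatment-regimen analysis, in contrast to the longitudinal primary model.
- SAP 4.4.2.3 defines longitudinal logistic regression separately, and Table GPHZ.4.2 uses it for hyperlipidemia.
- SAP 4.6.3.1 says the responder subgroup models take their within-patient covariance from 4.3.2.2, which contains none.

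**2. The plan's own power.** Inputs from Protocol 9.2: 87 per arm, 25% dropout, 25% versus 90% responders, Fisher's exact test, two-sided 0.025. Evaluable per arm: 87 × 0.75 = 65.25, taken as 65. Exact enumeration gives power above 0.9999. For the continuous endpoint (difference 11, SD 10), the noncentral t gives 0.99996. Both satisfy the stated figure of more than 90%, so the sample-size section is not in error.

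**3. What filling can do to the odds ratio.** The planned rates give (0.90/0.10) ÷ (0.25/0.75) = 27. Suppose every dropout is filled at an arm mean on the expected side of −5%:
- tirzepatide: 0.75 × 0.90 + 0.25 × 1 = 0.925
- placebo: 0.75 × 0.25 + 0.25 × 0 = 0.1875
- odds ratio: (0.925/0.075) ÷ (0.1875/0.8125) = 53

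**4. Simulation of the two tests.** Settings: 87 versus 87, Week 72 SD 10, 25% monotone dropout completely at random, two-sided 0.025. Assumptions not in the documents: five visits, AR-type correlation 0.85, no covariates, an EM fit standing in for the MMRM, and an exchangeable GEE standing in for the longitudinal logistic model. Responder rates follow from Φ((−5 − mean)/10). A placebo mean of +1.745 gives 25%; tirzepatide means of −2.5, −9.3 and −17.8 give 40%, 67% and 90%. The 67% case is a difference of 1.745 + 9.3 = 11.0 points, the plan's continuous effect.

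| Placebo vs tirzepatide (runs) | Protocol type: reject / median OR | SAP type, subject-level fill | SAP type, arm-mean fill |
|---|---|---|---|
| 25% vs 25% (600) | 2.3% / 1.04 | 4.5% / 1.00 | 1.5% / 1.00 |
| 25% vs 40% (300) | 34% / 1.99 | 50% / 2.15 | 28% / 1.85 |
| 25% vs 67% (200) | 100% / 6.4 | 100% / 7.4 | 100% / 13.4 |
| 25% vs 90% (150) | 100% / 29 | 100% / 42 | 100% / 62 |

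At 25% versus 40%, the Protocol-type and subject-level SAP-type decisions disagree in 18% of trials (standard error √(0.18 × 0.82/300) = 2.2 points).

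A second simulation used 11 visits, dropout at random and a GEE restricted to visits with no empty cell. At 25% versus 45% (120 trials) it gave 62% rejection for the SAP type and 50% for the longitudinal model, with 15% disagreement (standard error √(0.15 × 0.85/120) = 3.3 points).

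**5. Null behaviour.** The 4.5% has standard error √(0.045 × 0.955/600) = 0.8 points. A separate set of 6,000 null trials, also with 25% dropout and assumed trajectories, gave 3.5% for subject-level single imputation (standard error √(0.035 × 0.965/6000) = 0.24 points). It gave about 2% for observed-only data or arm-mean fill. Part of the apparent power gain of the SAP-type test in step 4 may therefore come from its inflated size.

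**6. Secondary endpoints.** Protocol 9.4.3.2 against SAP Tables GPHZ.4.2 and GPHZ.4.3:
- Weight-loss thresholds: longitudinal in the protocol, 4.3.2.2 logistic model in the SAP.
- IGT, NAFLD and the composite: single-visit logistic in both, but treatment plus sex in the protocol and all four strata in the SAP.
- Hyperlipidemia: longitudinal in both, so no change.

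SAP 4.9 lists neither of the two real changes.

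**The case against.** The strongest reply is that the protocol permits this. Section 9.4.1 lets method changes be described in the SAP or study report, and the same section allows other methods with details in the SAP. The SAP is written on protocol (b) and, on the main analysis, names one Week 72 model. Endpoint, hypotheses, alpha, analysis set and the missing-at-random efficacy estimand are unchanged. At the planned effect nothing turns on the choice.

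Much of that stands, and it rules out four stronger inferences a reader might draw.
- That the analyst is free to choose a test after seeing results. The SAP does name a model; what is missing is a record that it replaces the protocol's, and why.
- That a protocol amendment is mandatory. Neither document defines a principal feature, so this is a judgement.
- That the secondary binary endpoints were moved to single-visit models across the board. Hyperlipidemia was not, and IGT, NAFLD and the composite were never longitudinal.
- That the protocol model would break down because placebo may have no responders at Week 4. The documents give no Week 4 mean or SD, and nothing shows that the Week 72 contrast would be affected.

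The reply does not cover the silence of 4.9, the missing justification, the leftover covariance reference in 4.6.3.1, or the unspecified single imputation.

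**Conclusion.** The inconsistency is real and should be corrected, but it does not threaten the planned conclusion. At 25% versus 90%, and at an 11-point mean difference with SD 10, every version of the test rejected in every simulated trial. What changes is the reported odds ratio and its interval. Decisions can also differ at effects well below plan: 15% to 18% of trials at 40% to 45% responders on tirzepatide.

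The type I error excess, about 3.5% to 4.5% against 2.5%, is mild and belongs to the responder test taken alone with subject-level filling. Because the percent-change test must also pass, a dose with no effect on weight could not be declared superior more often than that test allows.

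All simulated figures rest on the stated assumptions about trajectories, correlation and dropout, and on GEE as a proxy for the protocol's model. The textual finding does not depend on them.

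**What to change.** Before unblinding:
- Name one primary responder model and one missing-data rule, identically in Protocol 9.4.3.1 and SAP 4.3.2.2.
- If the Week 72 logistic model is kept, replace the single predicted value with multiple imputation under missing at random, for example draws consistent with the MMRM combined by Rubin's rules, which SAP 4.3.3.1 already uses.
- Record and justify the change in SAP 4.9, and amend the protocol if the change is judged to touch a principal feature.
- Correct the covariance reference in SAP 4.6.3.1.
- Add to SAP 4.9 the two secondary changes: the model for the weight-loss thresholds, and the covariates for IGT, NAFLD and the composite.

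A longitudinal logistic sensitivity analysis is optional. The cost is wording in two documents and one multiple-imputation run; no new data are needed.
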